**Date prepared: June 18, 2013 (Ver. 1.1)**  
**Date revised: January 6, 2017 (Ver. 2.0)**  
**Date revised: February 27, 2018 (Ver. 2.1)**  
**(Date issued: April 1, 2018)**  
**(Portions changed: Underlined)**

**Protocol ID: A3921194**

## Introduction

Xeljanz® Tablets 5 mg (nonproprietary name: tofacitinib citrate; hereinafter referred to as “Xeljanz”) is a strong inhibitor of Janus kinase (JAK) created by Pfizer U.S., and has been approved as an antirheumatic drug. It has also been approved overseas, particularly in the U.S. in November 2012.

The approval of the indication, “treatment for patients with rheumatoid arthritis who showed inadequate response to conventional treatments” was granted under approval conditions to “conduct a use-result surveillance in all patients receiving Xeljanz until post-marketing data on a certain number of cases is accumulated so as to collect safety and effectiveness data as early as possible to take measures necessary for proper use” and “conduct appropriate post-marketing surveillance to adequately evaluate the safety of this product, and investigate the safety and effectiveness of long-term use including possible development of infections and related events.” Also, malignant tumors such as malignant lymphoma and solid cancer have been reported in clinical studies, while the causal relationship with Xeljanz is unknown. Therefore, in accordance with the approval conditions, and taking into consideration the fact that Xeljanz is a new drug with a new mechanism of action, and that serious infection has been identified as a risk associated with Xeljanz, “Xeljanz® Tablets 5 mg Specific Use-result Surveillance (all-cases survey)” (hereinafter referred to as “Surveillance”) with a control group shall be conducted.

This Surveillance is conducted by Pfizer Japan Inc. (hereinafter referred to as “Sponsor”), and is intended to investigate the actual use status of Xeljanz to confirm the occurrence of each adverse reaction associated with Xeljanz (for which, malignant tumors and serious infections will be compared with a control group), and to detect or confirm effectiveness and other safety data concerning Xeljanz. The information collected in this Surveillance will be used to prepare documents to be included in the Proper-Use Information and prepare documents to be included in the application for reexamination.

This Surveillance shall be conducted in compliance with the “Ordinance concerning Standards for Conducting Post-Marketing Surveillance and Studies on Pharmaceutical Products” (MHLW Ordinance No. 171 dated December 20, 2004). Data obtained from the patients enrolled in this Surveillance will be reported to the MHLW pursuant to the Pharmaceuticals and Medical Devices Act; pertinent to which, data may be publicly posted in MHLW’s “Pharmaceutical and Medical Device Safety Information” and Pharmaceuticals and Medical Devices Agency’s “Pharmaceuticals and Medical Devices Information Website (<http://www.info.pmda.go.jp>)” as a listing of patients, which will present the names of drugs, adverse reactions, gender, age (increment of 10 years), and other relevant information. Furthermore, data collected may also be disclosed if the MHLW is required to disclose such information in accordance with the “Act on Access to Information Held by Administrative Organs” (Law No. 42 dated May 14, 1999); provided that in no event will the names of physicians, medical institutions, and other personal information be subject to such disclosure, nor will it be posted or disclosed in any form or shape.

## 1 Objective

The objective of this Surveillance is to verify the following subject matters concerning Xeljanz® Tablets (hereinafter referred to as “Xeljanz”) under post-marketing actual status of use.

- 1) Occurrence of adverse reactions, factors that may potentially affect safety, and effectiveness
- 2) Long-term safety (particularly, malignant tumors and serious infections) and effectiveness

Occurrences of malignant tumors and serious infections will be compared with a control group.

### [Approval conditions]

[figure not shown]
1. To conduct a use-result surveillance in all patients receiving Xeljanz until post-marketing data on a certain number of cases is accumulated so as to collect safety and effectiveness data as early as possible to take measures necessary for proper use.
2. To conduct appropriate post-marketing surveillance to adequately evaluate the safety of Xeljanz, and investigate the safety and effectiveness of long-term use including possible development of infections and related events.

## 2 Subjects

Among rheumatoid arthritis patients with poorly controlled disease in spite of continuous use of a methotrexate preparation (hereinafter, MTX) in a dosage exceeding 8 mg/week for 3 months or more, those meeting the following criteria:

- 1) All patients who receive Xeljanz (Xeljanz group)
- 2) Patients who have begun pharmacotherapy with another drug\* (control group)

\*Patients with no experience of treatment with Xeljanz (Patients participating in clinical trial cannot be registered in the control group)

When using Xeljanz, refer to “Guidelines for the use of tofacitinib in all-cases post-marketing surveillance” (revised version on June 29, 2014) (Japan College of Rheumatology) (hereinafter, “tofacitinib use guidelines”). Please consider using a pharmacotherapy other than Xeljanz for patients who do not meet the criteria shown below.

[Target patients]

1. Rheumatoid arthritis patients with poorly controlled disease in spite of continuous use of a methotrexate preparation (MTX) in a dosage exceeding 8 mg/week for 3 months or more. Patients with the above treatment history after February 23, 2011 when the approved dosage for MTX was increased to 16 mg/week are targeted. However, it is desirable not to target patients to whom MTX cannot be administered from the safety perspectives at this point, in principle.
  - Painful joint count of 6 or more
  - Swollen joint count of 6 or more
  - CRP of 2.0 mg/dL or more or ESR of 28 mm/hr or more
 Even if patient does not meet the 3 criteria above, consider use if there is moderate or higher activity for any of
  - DAS28-ESR, SDAI, and CDAI.
2. Moreover, out of consideration for safety with respect to opportunistic infections, it is strongly recommended that the following 3 criteria be met.
  - Peripheral blood count of 4000/mm^3 or more
  - Peripheral lymphocyte count of 1000/mm^3 or more
  - Negative for blood β-D-glucan

Excerpted from “tofacitinib use guidelines”

The indication and dose regimen for this Surveillance are as follows: (This surveillance targets rheumatoid arthritis patients with poorly controlled disease in spite of continuous use of a methotrexate preparation (MTX) in a dosage exceeding 8 mg/week for 3 months or more.)

- Indication: Patients with rheumatoid arthritis who showed inadequate response to conventional treatments
- Dosage and Administration: As a standard therapy, a patient should receive a daily oral administration of tofacitinib 5 mg BID.

Refer to the most updated package insert and “tofacitinib use guidelines” when administering Xeljanz.

### 3 Target sample size

Target sample size: Subjects who meet the conditions in “2. Subjects” for each group and the sample size is shown below.

#### 1) Xeljanz group: 4000 subjects for safety analysis

· The target sample size is set to be 4000 subjects by adding a certain sample size a) b) of  $\geq 3000$  subjects beginning from the start of registration (3-year observation) to the subsequent number of subjects (6-month observation period). See “6.5 observation period” for more information. However, even if Xeljanz is administered to subjects who do not meet the conditions described in “2. Subjects” for inevitable reason(s), while such subjects will not be included in the above sample size, the request to enroll subjects and complete survey forms will be made for subjects in the Xeljanz group for the sake of all-cases survey.

#### 2) Control group: A certain sample size a) b) of $\geq 2000$ subjects for safety analysis

#### [Remarks]

a) The sample size in both groups will be set to be the number of subjects for whom the degree of statistical accuracy described in [Rationale for sample size] is maintainable. See the Appendix for more information.

b) The registration period until a certain sample size is reached will be the same period for both groups.

#### [Rationale for sample size]

The incidence of malignant tumor associated with Xeljanz in a domestic long-term administration study (Study No. A3921041) was 1.16 (/100 person-year). The drop-out rate in clinical studies was 31% among subjects who transferred from the domestic Phase II study (Study No. A3921039) to the domestic long-term administration study (Study No. A3921041) (treatment period: approximately 3 years), and 14% among subjects who transferred from another domestic Phase II study (Study No. A3921040) (treatment period: approximately 1.4 years); based on which, the drop-out rate at the completion of 3-year observation in daily medical practice is estimated to be approximately 50%.

If 4000 patients were to be enrolled in the Xeljanz group, the target events should be confirmable in 104 patients based on the incidence of malignant tumor in Japanese subjects, which was 1.16 (/100 person-year).

Next, assuming that 4000 patients would be enrolled in the Xeljanz group and the incidence of malignant tumor in the control group would be equivalent to the Xeljanz group, at least 2000 subjects would need to be enrolled in the control group in order to enable a statistically appropriate inter-group comparison; thus, a sample size of 2000 subjects was selected for control.

Depending on the progress of registration, if the registered number of patients in either group significantly exceeds the above number earlier than the other group, a sample size with 3-year observation period can be changed to the combination of a sample size for whom the degree of statistical accuracy is maintainable if it is compared with 4000

patients in the Xeljanz group and 2000 patients in the control group (see the Appended Table). Also, the registration period for patients in the inter-group comparison needs to be the same.

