## 6.5 Observation period

### [1] Xeljanz group:

- (1) Registered subjects up to a certain sample size exceeding 3000 subjects from the start of registration: 3 years (36 months) from the date of treatment start
- (2) Registered subjects after the above (1): Only 6 months from the date of treatment start

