*The incidence of malignant tumors after administration of Xeljanz in a Japanese long-term study (Study No. A3921041) is 1.16 (/100 patient-years). Since the dropout rate in clinical studies is 31% in subjects who proceeded to the Japanese long-term study (Study No. A3921041) from a Japanese phase II study (Study No. A3921039) (duration of treatment, 3 years) and 14% in subjects who proceeded from a Japanese phase II study (Study No. A3921040) (duration of treatment, 1.4 years), the dropout rate at the completion of 3-year observation under the actual use conditions in routine practice is assumed to be about 50%.*

*If the number of patients in the Xeljanz group is set at 4000, events can be confirmed in 104 patients based on the incidence of malignant tumors in Japanese patients of 1.16 (/100 patient-years).*

*Meanwhile, if the number of patients in the Xeljanz group is set at 4000 and the incidence of malignant tumors in the control group is assumed to be comparable to that in the Xeljanz group, at least 2000 patients will be required to allow a statistically valid comparison between the groups. Therefore, the number of patients in the control group was set at 2000.*

*Depending on the progress of registration, if the registered number of patients in either group significantly exceeds the above number earlier than the other group, a sample size with 3-year observation period can be changed to the combination of a sample size for whom the degree of statistical accuracy is maintainable if it is compared with 4000 patients in the Xeljanz group and 2000 patients in the control group (see the Appended Table). Also, the registration period for patients in the inter-group comparison needs to be the same.*

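### The expected 104 Xeljanz malignancies applies only if all 4000 patients have 3-year observation; the other eight permitted Appendix rows give about 101 down to 84 on the same inputs

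*Protocol*

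**What the plan says.** The rationale under Protocol section 3 takes a malignancy incidence that "was 1.16 (/100 person-year). The drop-out rate in clinical studies was 31"% in one feeder study and 14% in another. It then assumes that "the drop-out rate at the completion of 3-year observation in daily medical practice is estimated to be approximately 50"%. From these it concludes, for an enrolment of 4000, that "the target events should be confirmable in 104 patients based on the incidence of malignant tumor in Japanese subjects". SAP section 2.1 carries the same statement: "events can be confirmed in 104 patients based on the incidence of malignant tumors in Japanese patients of 1.16" per 100 patient-years.

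Protocol section 3, item 1, builds the 4000 from two blocks, adding "subjects beginning from the start of registration (3-year observation) to the subsequent number of subjects (6-month observation period"). Section 6.5 sets the follow-up of each block. The first is "Registered subjects up to a certain sample size exceeding 3000 subjects from the start of registration: 3 years (36 months) from the date of treatment" (last word omitted). The second is "Registered subjects after the above (1): Only 6 months from the date of treatment start". The notes to the booklet table in section 6.5 and to section 7.7 add that the second block gets no follow-up survey.

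The Appendix lists nine permitted combinations, from 2000 control / 4000 Xeljanz at 3 years / 0 at 6 months, to 2400 / 3000 / 1000. The Xeljanz total is 4000 in every row. The rationale says that the alternatives are meant to preserve the precision of the 4000 versus 2000 comparison. No expected event count is given for any alternative row.

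**The concern.** The rationale ties 104 simply to enrolling 4000 Xeljanz patients. Every Appendix row enrols 4000, so a reader would apply 104 to any of them. Yet in eight of the nine rows some of the 4000 are watched for 6 months only, and no malignancy after that point is collected for them. The figure appears not to have been qualified for the two-block design.

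It is the only expected event count given for malignancy, which the objectives name together with serious infections as a focus of long-term safety. Several planned results depend on the absolute number of Xeljanz events rather than on the contrast with control: the single-group rate with its exact interval (SAP 8.1.5), the standardized incidence ratio overall and for eleven cancer types (SAP 8.2.3.1.1), and rates by time period (SAP 8.2.3.2).

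**Working it through.** **Inputs.** Incidence 1.16 per 100 person-years, drop-out of about 50% at 3 years and N = 4000 (Protocol section 3, rationale); observation of 36 or 6 months (section 6.5); the nine combinations (Appendix). The shape of drop-out over time is not stated.

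**Reproducing 104.** Expected events = N × mean years observed × 0.0116. If drop-out is linear to 50% at 3 years, mean observation is 3 × (1 + 0.5)/2 = 2.25 years. Then 4000 × 2.25 × 0.0116 = 104.4, which matches.

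Other readings for 4000 patients at 3 years do not match: exponential drop-out 100.4, no drop-out 139.2, completers only 69.6. The product 3000 × 3 × 0.0116 is also 104.4, but it would need 3000 patients and no drop-out, against the stated 4000 and 50%. So 104 rests on 4000 patients all scheduled for 3 years, and linear drop-out is an inference from that match.

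**Applying the same inputs to the Appendix.** Mean observation over 6 months, on the same linear path, is 0.5 − (0.5/3) × 0.5²/2 = 0.479 years. Control events use 2.25 years and the same rate, as the rationale assumes. The last column is √(1/events in 3-year Xeljanz + 1/events in control).

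| Control | Xeljanz 3 y | Xeljanz 6 m | Events, 3 y | Events, 6 m | Xeljanz total | Control events | SE of log rate ratio |
|---|---|---|---|---|---|---|---|
| 2000 | 4000 | 0 | 104.4 | 0.0 | 104.4 | 52.2 | 0.1695 |
| 2050 | 3814 | 186 | 99.5 | 1.0 | 100.6 | 53.5 | 0.1695 |
| 2100 | 3653 | 347 | 95.3 | 1.9 | 97.3 | 54.8 | 0.1695 |
| 2150 | 3511 | 489 | 91.6 | 2.7 | 94.4 | 56.1 | 0.1695 |
| 2200 | 3385 | 615 | 88.3 | 3.4 | 91.8 | 57.4 | 0.1695 |
| 2250 | 3273 | 727 | 85.4 | 4.0 | 89.5 | 58.7 | 0.1695 |
| 2300 | 3173 | 827 | 82.8 | 4.6 | 87.4 | 60.0 | 0.1695 |
| 2350 | 3082 | 918 | 80.4 | 5.1 | 85.5 | 61.3 | 0.1695 |
| 2400 | 3000 | 1000 | 78.3 | 5.6 | 83.9 | 62.6 | 0.1695 |

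The comparative analysis set in SAP 5.1.2 is limited to patients with 3-year scheduled observation, so the relevant Xeljanz count there is the fourth column: 104.4 down to 78.3.

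**Sensitivity to drop-out.** For rows 1 and 9 the totals are:

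- exponential to 50%: 100.4 and 80.8
- linear to 31%: 117.6 and 93.9
- linear to 60%: 97.4 and 78.6
- no drop-out at all: 139.2 and 3000 × 3 × 0.0116 + 1000 × 0.5 × 0.0116 = 110.2

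The level moves, but row 9 stays about 19% to 21% below row 1 throughout.

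**Effect on single-group precision.** With the exact interval of SAP 8.1.5 at a rate of 1.16 per 100 person-years, the 95% limits are about 0.95–1.41 with 104.4 events (9000 person-years), 0.93–1.44 with 83.9, and 0.92–1.45 with 78.3. The log-scale standard error, 1/√events, rises from 0.098 to 0.109 (about 12%) and 0.113 (about 15%).

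**The case against.** The rationale is conditional. It describes a reference case of 4000 versus 2000, gets the reference figure right, and then says separately that equivalent combinations may be used. The 4000 + 0 row is still permitted, so 104 is correct for a design that the protocol allows. A reader might infer an arithmetic mistake; the documents do not support that.

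A reader might also infer that the comparison with control loses power when the 3-year Xeljanz block shrinks. It does not. The control group grows to compensate: 1/4000 + 1/2000 = 1/3000 + 1/2400 = 0.00075, and the intermediate rows agree to rounding. The stated sizing criterion is met in every row. No decision rule uses 104, and SAP section 4 calls the tests exploratory. The SAP's repetition is not a separate error either, since SAP section 2 says that it cites protocol text.

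Three further points limit the size of the concern.

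- Malignancy follow-up in the 3-year block continues after treatment is discontinued, with exceptions such as death, no revisit or transfer (Protocol 6.5 and 7.7), and the SAP's primary malignancy definition covers the overall observation period. Person-time could therefore exceed 2.25 years per patient. This would raise the count in every row and leave the gap between rows.
- The Appendix rows are minimums.
- Survey forms are also collected from Xeljanz patients outside the target population, on top of the 4000. They enter the wider SAP safety set, so the reduction concerns the target population rather than all Xeljanz data.

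All of this stands. It does not answer the narrower point that the stated yield is attached to 4000 enrolled patients without saying that it needs 3-year observation of all of them.

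**Conclusion.** The point holds as a figure left unqualified under a design with two observation lengths. On the documents' own inputs, 104 belongs to the first Appendix row only. The other eight give 100.6 down to 83.9, and the last has 78.3 events in the 3-year comparative set. The largest shortfall is about 20 events (104.4 − 83.9 = 20.5, or 20%) and arises only at the extreme row.

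The consequence is modest: a single-group interval of about 0.93–1.44 instead of 0.95–1.41, and proportionately thinner data for standardized incidence ratios and cancer types. Between-group precision is unchanged, under equal rates in the two groups.

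The absolute counts rest on linear drop-out to 50%, which the documents do not state. A reader should not take 84 as a forecast of what the surveillance will observe. It is what the plan's own calculation gives for the 3000 + 1000 row.

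**What to change.** In the protocol rationale, and in SAP section 2.1 where it is cited:

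- State that 104 applies to 4000 Xeljanz patients all scheduled for 3-year observation.
- Restate the expected count as about 84 to 104 depending on the Appendix row, or 78 to 104 among 3-year patients.
- State the assumption behind these figures (1.16 per 100 person-years, drop-out linear to 50% at 3 years), and note that follow-up after discontinuation may raise them.

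An expected-events column per group in the Appendix would be a convenient way to show this, but it is optional. The cost is a sentence or two and a less favourable headline figure. Enrolment and analysis stay as they are.

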## 4 Sites conducting this Surveillance

This Surveillance will be conducted in all sites (departments) where Xeljanz is prescribed; provided that doctors prescribing Xeljanz must meet the below criteria and consent to "Confirmation of Cooperation to Surveillance."

### 4.1 Site requirements:

Sites must meet both of the following conditions 1) to 2):

- 1) Cooperate with Xeljanz Tablets 5mg Specific Use-result Surveillance (hereinafter referred to as "Surveillance");
- 2) Provide urgent medical intervention, etc. to adverse reactions that may occur in patients using Xeljanz (including the sites\* which may provide in cooperation with other medial facilities).

\*When diagnosing and treating serious infections, tuberculosis, or malignant tumors in collaboration with other medial facilities, information on safety measures and treatment for adverse drug reactions associated with Xeljanz will be shared with the collaborating medial facilities, and the system of cooperation will be confirmed.

### 4.2 Doctor requirements:

Doctors must meet all of the following conditions [1] to [5]:

[1] A doctor must meet all of the following Items (1) to (3):

- (1) Is a rheumatologist certified by the Japan Rheumatism Association;
- (2) Is a rheumatologist certified by the Japanese Orthopaedic Association; or
- (3) Has taken part in clinical study(s) of Xeljanz.

[2] Doctors with abundant experience in using methotrexate drug

[3] Doctors with abundant experience in using biological drugs

[4] Doctors who can cooperate with this Surveillance

[5] Doctors who are available for interview with Medical Sponsor

## 5 Duration of surveillance

Duration of surveillance:

From the date marketing of Xeljanz begins to the completion of assessment by regulatory authorities

Enrollment period: From initial marketing for Xeljanz to lifting approval conditions for all-cases survey

Completion of survey forms for the Xeljanz group will no longer be mandated after reaching the registration of 4000 subjectsc) in the Xeljanz group, which is the target sample size, after the approval from regulatory authorities is obtained. Meanwhile, registration will be continued until the final assessment is made by regulatory authorities.

For the control group, both completion of survey forms and registration will no longer be mandated after the target sample size is reached and the approval from regulatory authorities is obtained.

\*The results of collecting and analyzing 6-months data on the 4000 subjectsc) in the Xeljanz group will be submitted to the regulatory authorities together with the results of collecting and analyzing 6-months data on the subjects in the Xeljanz group who do not meet the conditions described in "2. Subjects" and the control group.

c) Subjects who meet the conditions described in "2. Subjects".

